# Milestones

- 1. Month 19: Behaviour change targets
- 2. Month 21: Training materials in an online training package
- 3. Month 21: Self-report questionnaire and skills checklist
- 4. Month 21: Measure of adherence to the intervention.

WP4: Working with electronic databases to test search strategy for identifying repeat self-harm and healthcare contacts

WP4 Objectives:

Version 8.0, 13/08/2021, ASsuRED study protocol IRAS no: 257373 Page 26 of 46

- 1. Identify the different electronic records systems across the ED and hospital trial sites
- 2. Test the search strategy for identifying repeat self-harm across the 4 sites in WP2
- 3. Test the procedures for identifying healthcare contacts/resource use from electronic databases to inform the economic evaluation (e.g., types of contacts with patient, duration of consultations/contacts; type of personnel involved).

In preparation for a future trial, WP4 will identify the different IT systems across the ED trial sites. We will test our search strategy for identifying repeat self-harm and healthcare contacts/resource use by patients for the four sites in WP2, with the consent of participants from WP2. It is possible to interrogate the databases successfully as demonstrated in previous studies (detailed below). However, we will check the search strategy in different electronic record systems to identify any issues that require addressing before the trial. The ED electronic records will be screened by a member of the research team, and details of repeat self-harm attendances will be extracted and entered onto an excel spreadsheet, with details of the number of repeat attendance(s) and the date(s).

Self-harm will be identified by searching ED electronic records, using the same approach as the Multicentre Study of self-harm in England (Hawton et al. 2015), which identifies 98-100% of self-harm cases (Clements et al. 2016): researchers will search records using an extensive list of search terms (including Self-Harm, Limb Problems, Overdose/Poisoning, Unwell Adult, Mental Illness, Behaving Strangely, Collapsed Adult, Wounds, Burns/Scalds) to identify possible self-harm cases. This is an inclusive approach so that cases not clinically coded as self-harm are still identified. Each record will then be screened for evidence that the presentation was due to self-harm. An end point committee of clinical experts will review the data to identify self-harm. The end point committee will be blinded to treatment allocation for the study duration. They will be given clear criteria, and the evidence for these criteria will be documented so that the decisions will be transparent and can be checked. Any subjective element would be the same in both arms.

Also under WP4, we will finalize plans for data collection to support economic analysis. This is likely to require combination between centrally held data (NHS Digital); data from local information systems and data collected directly from patients, practitioners and researchers contributing to the study. We will initiate NHS Digital data request for the participants' healthcare data to support trial analysis.

[figure not shown]
### Milestones:

- 1. Month 21: Self-harm search strategy tested across sites for the trial
- 2. Month 21: Procedures for identifying resources use tested

# 7. STUDY PROCEDURES

### Recruitment

Version 8.0, 13/08/2021, ASsuRED study protocol IRAS no: 257373 Page 27 of 46

# WP1 -practitioner focus groups

Practitioners will be recruited in the participating EDs and Royal Exeter and Devon NHS Foundation Trust. GPs will be recruited in primary care via NHS Trust networks and ED practitioner contacts.

# WP1 -patients and carers

Patients and carers will be recruited by distributing posters and leaflets via service user organisations, PPI networks and wider community settings. We will recruit via EDs (Royal London Hospital, Homerton Hospital) and specific PPI groups and networks. The Service User and Carer Advisory Group on Research (SUGAR) has recommended the following channels:

[figure not shown]
- Mind in Stratford
- o Homeless shelters
- Generation R young people's patient research ambassadors
- Asian community Mosque Whitechapel: East London Mosque outreach centre
- Campaign Against Living Miserably
- Self-harm group, Isle of Dogs
- o Groups specifically for men
- LGBT groups
- Mind self-harm group

# WP2 -Feasibility study and interviews

Patients presenting with self-harm will be asked to participate. People presenting with self-harm are referred to a specialist mental health team called a psychiatric liaison team either by (1) a triage nurse in the ED or (2) from a brief stay inpatient ward (e.g. an acute medical unit). A healthcare practitioner will assess whether the patient has capacity to consent to participate in a research study and ask potential participants if they are willing to be approached by a researcher. The two patient pathways are as follows:

- 1) People who attend the ED are first seen by a triage nurse and then referred to the psychiatric liaison team. The practitioner in the psychiatric liaison team will assess whether they deem the person has capacity to consider participating in a research study and if they have capacity, the liaison practitioner will ask if they are happy for a researcher to approach them.
- 2) Patients are also referred to the psychiatry liaison team from inpatient wards. A nurse in the inpatient ward or psychiatric liaison practitioner will initially approach the patient to assess capacity to consent to participate. If they have capacity, the practitioner will ask if they are happy for a researcher to approach them and talk to them about the study.

Version 8.0, 13/08/2021, ASsuRED study protocol IRAS no: 257373 Page 28 of 46

# **Informed Consent Procedures**

Consent forms will be sought from all participants, and copies will be stored in the site file, medical records and a copy will be given to the participant.

# **Practitioners**:

Practitioners will be approached by researchers who will discuss the study (e.g., in team meetings), provide written information and an opportunity to ask questions and receive further information. Researchers will obtain written informed consent from those who are interested in taking part. Practitioners will be informed of which study arm they are allocated to prior to consent (i.e. the intervention or control arm). Separate consent and information sheets will be provided for practitioners in each study arm.

# Patients:

[figure not shown]
Two consent procedures will be in place: one for sites recruiting to the intervention arm only, and a second for sites recruiting to both the control and intervention arms. Consent will take a two-step approach. This will allow us to assess how to maximise recruitment in the future RCT.

Step 1: Consent procedures for sites recruiting to the intervention arm only: Patients will initially be approached by a practitioner in the liaison psychiatry team and asked if they are interested in taking part in the study. They will provide the participant with the Summary PIS and will obtain verbal consent from the participant that they wish to take part. The consent may also be taken by a researcher, if they are on-site when the patient presents to the ED. Participants will be informed they will be offered the intervention.

Step 1: Consent procedures for sites recruiting to the intervention and control arms: Patients will initially be approached by a generalist practitioner in the ED and asked if they are interested in taking part in the study. They will provide the participant with the Summary PIS and will obtain verbal consent from the participant that they wish to take part. The consent may also be taken by a researcher, if they are on-site when the patient presents to the ED. Based on the principle of equipoise, patients will be informed that practitioners have been trained in different ways of conducting assessments and follow up case, and they will use the approach they have been trained in.

Step 2: After potential participants verbally agree with a practitioner to speak to a researcher and they have had their psychosocial assessment, a researcher will discuss the study with the participant. At this point the urgency will have passed so the participant will be given the full length Patient Information Sheet (PIS) by the researcher and they will have time to read it. They will be given the opportunity to ask questions or for further information about the study. Written informed consent will then be obtained from those who wish to take part. Participants will be considered enrolled in the study after written consent is obtained.

Version 8.0, 13/08/2021, ASsuRED study protocol IRAS no: 257373 Page 29 of 46

We will seek written consent in WP2 from patients to (a) participate in interviews after their meeting with a psychiatric liaison practitioner (b) complete outcome measures at 6 months and (c) access the patient's medical records to identify repeat self-harm and healthcare resource during the 6-month follow-up period and 6 months preceding recruitment for WP4.

Covid-19: During the pandemic, researchers will not be on-site to take consent unless permitted by the site and a risk assessment is in place. Thus, the initial approach will be undertaken by a practitioner who will introduce the study with the Summary PIS and will take verbal consent to take part in the study. The research team and LEAP have prepared a video to introduce the team and study, which the practitioner can play to patients prior to asking for verbal consent. This will also be available in audio format, which can be used if preferred by participants. After verbal consent is obtained, written consent will be obtained either: (1) by an onsite member of the team (either researcher or member of the clinical team trained in obtaining informed consent) or (2) the researcher will contact the person to take written consent via a secure REDCap database. If it is not possible to obtain written consent, audio-recorded verbal consent will be obtained (e.g. if they do not wish to meet in person and do not have internet access), by asking the participant whether they agree to each clause in the consent forms.

# Carers:

Carers accompanying the patient, will be asked to participate only after the patient has agreed to participate and has consented for their carer(s) to be approached to consider participating. They will be provided with the carers information sheet, an opportunity to ask questions about the study and if they agree to participate, will provide written informed consent.

[figure not shown]
Research data will be collected in quiet rooms within facilities of participating Trusts/Universities. Researchers will follow the lone worker policy of their respective participating NHS trusts.

# **Payment**

For WP1, patients and carers will receive a £20 voucher for participating in the focus group. Practitioner participants will not be reimbursed for their time as the research will take place during their working hours.

For WP2, patients taking part in baseline and follow-up interviews will be offered £15 cash or voucher as a reimbursement for their time for each interview (maximum £30). In WP2, carers will not be offered reimbursement as they will be in a supporting role for their friend/ family member. Practitioner participants will not be reimbursed for their time as the research will take place during their working hours. The participation of the practitioners will be discussed with their line managers and team leads.

Version 8.0, 13/08/2021, ASsuRED study protocol IRAS no: 257373 Page 30 of 46

We will be unable to pay travel expenses, but meetings will be arranged at a place convenient to participants.

# 8. ETHICS

Ethical issues arise from the participation of people at risk of further self-harm or suicide who present in crisis at the emergency department. There are four main issues:

### 1. Informed consent

The procedures for approaching people, providing information about the study and obtaining consent have been developed with people with lived experience of suicidal thoughts and suicide attempts attending the ED, which include members of the Lived Experience Group (LEG) at the University of Exeter and the Lived Experience Advisory Panel (LEAP), Recovery Devon.

In the proposed study, there will be a three-step consent process, to reaffirm consent throughout the process:

- Consent will initially be obtained verbally to minimize burden on patient at the point at which they are in crisis
- ii. Consent will be reaffirmed during assessment by the mental health practitioner (Liaison Psychiatry team member).
- iii. Written consent will be obtained by the researcher after the assessment with the mental health practitioner, at which time the participant will have time to decide whether they wish to take part or withdraw.

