# WP2 (3) Pilot patient-rated outcome measures

We will assess the acceptability of outcome measures and the burden on patients, including self-reported self-harm. This will be conducted in the ED, over the phone or by video meeting or in patients' homes (according to preference). Participants will be given the option of completing self-report measures on paper or online via a secure REDCap database. Researchers will interview patients twice to collect outcome measures: once at baseline on the day they attend the ED/ within one week of attending the ED and once after 6 months. We will test disease-specific and more generic quality-of-life outcome measures. We will collect data on response rates and feedback on the following outcome measures:

Version 8.0, 13/08/2021, ASsuRED study protocol IRAS no: 257373 Page 20 of 46

- the therapeutic relationship, self-rated by patients on the Helping Alliance Scale (Priebe & Gruyters, 1993)
- suicide severity, administered by researchers on the Columbia–Suicide Severity Rating scale (Posner et al. 2011)
- quality of life measured with CORE-OM (Barkham et al. 2001, Mavranezouli et al. 2011)
- Social outcomes, measured with the Social Outcomes Index (SIX) (Priebe, Watzke, Hansson, & Burns, 2008)
- Quality of Life, measured with the Manchester Short Assessment of Quality of Life (MANSA; Priebe, Huxley, Knight, & Evans, 1999)
- Experiences of attending Accident & Emergency Questionnaire, devised for this study

Each month for six months after they leave the ED, participants will be sent an email to an electronic survey to collect:

self-reported self-harm data

Self-reported self-harm will be collected via an online survey: participants will receive an email inviting them to complete the survey. This survey has been co-designed with the Lived Experience Advisory Panel.

At the end of the 6 month intervention period, we will collect data on:

 Repeat self-harm identified by searching ED electronic records (using the gold standard approach developed in the Multicentre Study of self-harm in England (Clements et al. 2016).

Death by suicide, i.e., cause of death is intentional self-harm or undetermined intent derived from NHS/ local authority/coroner records.

[figure not shown]

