# Methods

Each practitioner will implement the intervention with one patient each for three months (month 10-12) and provide feedback to refine the intervention. They will then implement the intervention with one further patient for 3 months (13-15) and provide feedback to refine the intervention. Finally, they will implement the intervention with one further patients for 3 months (16-18) and provide feedback to refine the intervention. Practitioners will stay in follow-up contact with each patient, and a carer if available, for up to 9 months. They will meet with the patient three times over the first two months, and will send three personalised letters to the patient for the seven months after their final meeting. Carers will be family members, partners, carers or friends involved in supporting the patient.

Subject to ethical approval and written informed consent, each practitioner will videorecord meetings with patients each in the ED and audio record the subsequent followup phone contacts to explore how the intervention is being implemented and adherence to the intervention. Practitioners will keep meeting notes and a diary to record the frequency, mode, duration and content of contacts with patients during the intervention. We will record how many patients presented to the ED during this time who would be eligible for the intervention.

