Consent: Given that people will be presenting in crisis and we will record sensitive information (outcome data, interviews, clinical meetings), we will adopt a three-step consent process. A mental health practitioner will ask the patient if they are willing to be approached by a researcher. Capacity to consent to taking part in research will be assessed using the study's Capacity Checklist (available from the Study Coordinator, on request). If patients consent to participate after being fully informed, the researcher will obtain written informed consent. The mental health practitioner will confirm consent when they assess the patient. Finally, the researcher will re-affirm consent after the clinical assessment with the mental health practitioner. When the researchers first approach the patients to explain the study and obtain informed consent, they will explain how each type of data will be used and stored. This will be clearly described in the information sheets and written consent forms provided to patients. In our ongoing Relate study (PI [name], 17/LO/1234), participants were interviewed within 2 weeks of their meeting in the ED with a mental health practitioner. During the interview they were asked for feedback on their experience of participating in the research. They suggested that it was a positive experience and all interviewees stated that the reason for wanting to participate was to help others with mental health problems: "if it can help somebody else then I'm quite happy to do it" (Patient); "if someone sees it [video recording of the clinical assessment] then they'll learn something won't they?". On being video-recorded, they stated: "if it's a good thing that they're there and being recorded then I'd like to help with that" and "I didn't even notice the cameras were there".

Recording practitioner-patient meetings in the ED/ follow-up contacts: Researching and recording sensitive mental health practitioner-patient meetings after self-harm could potentially add further distress to people. During these contacts, practitioners will be present and will be alert to this possibility and the potential need to reassure patients or terminate the research process if it is adding to the person's distress.

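### Written consent comes after the ED assessment in Sections 7 and 8 but before it in Section 9, and WP2 requires written consent for the video of that assessment

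*Protocol*

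**What the plan says.** Four parts of the protocol deal with the order of consent, assessment and filming for WP2 patients.

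- **Section 7, Informed Consent Procedures, Patients.** Consent is described as two-step. Step 1 is a verbal agreement after a summary information sheet. Step 2 takes place once "they have had their psychosocial assessment, a researcher will discuss the study with the participant"; the full information sheet is given at that point. Then: "Written informed consent will then be obtained from those who wish to take part". Enrolment is tied to the same moment: "Participants will be considered enrolled in the study after written consent is obtained".
- **Section 8, 1. Informed consent.** Three steps: verbal consent, reaffirmation during the assessment, and finally "Written consent will be obtained by the researcher after the assessment with the mental health practitioner".
- **Section 9, Consent.** Also three steps, in a different order. The researcher obtains written consent, then "The mental health practitioner will confirm consent when they assess the patient", and the researcher re-affirms consent after the assessment.
- **Section 6, WP2 (4) Methods.** "Subject to ethical approval and written informed consent, each practitioner will videorecord meetings with patients each in the ED".

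Two further places bear on the recording. Section 8, item 3, has researchers explain how recordings are used and stored when they first approach the participant. The Audio/video recordings paragraph of Section 11 asks only for participants' permission.

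On timing of measures, WP2 (3) has patients interviewed "once at baseline on the day they attend the ED/ within one week of attending the ED" and again after 6 months.

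**The concern.** Sites cannot follow Sections 7, 8 and 9 together, and the order they choose decides whether the WP2 Methods condition on filming is met. The ED assessment is the meeting to be filmed. If written consent is taken only afterwards, a site must either film a patient in crisis before the consent that the protocol requires, or not film.

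The first course puts the validity of consent for an identifiable recording in doubt. The second loses recordings that feed the core-skills analysis in WP2 (5) and the comparison of self-reported with observer-rated competence in WP3. WP2 (5) itself notes that nonverbal communication can be observed only on video.

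A secondary consequence concerns the baseline measures. Enhanced assessment and safety planning in the ED are components of the intervention (Section 4, Theoretical Framework; WP1 (1)). If enrolment waits for written consent and written consent waits for the assessment, measures taken after enrolment are not pre-intervention values in the intervention arm.

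**Working it through.** The check is mainly one of sequence. There is no planned statistical figure to reproduce.

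**Order A (Section 7 Step 2 and Section 8 item 1):** verbal consent → ED assessment → written consent and enrolment → first questionnaires.

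**Order B (Section 9):** written consent → ED assessment, with the practitioner confirming consent → re-affirmation by the researcher.

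1. *Filming against the WP2 Methods condition.* Under A, written consent comes after the meeting to be filmed, so the condition is not met at the time of filming. Under B it is met.
2. *Explanation of the video by a researcher (Section 8, item 3).* Under A, the researcher's discussion is at Step 2, after the assessment, unless a researcher is on site at Step 1. The Covid-19 paragraph of Section 7 keeps researchers off site unless the site permits it and a risk assessment is in place, so the exception may be uncommon. Under B the explanation comes first.
3. *Standard of consent for recording.* WP2 Methods: written informed consent. Section 11: permission. These are different standards for the same recording.
4. *Number of steps.* Section 7: two. Sections 8 and 9: three.
5. *Recordings exposed.* WP3 has 15 practitioners film meetings with about 2 patients each: 15 × 2 = 30. WP3 itself gives up to 32 cases. Either way it is about 30.
6. *First questionnaires.* Under A, enrolment follows the ED assessment, so measures taken after enrolment follow the first intervention contact. The intervention arm has 15 practitioners × up to 3 patients = up to 45. The 15 control patients receive usual care, so the point does not apply to them. Under B the questionnaires could come first, but nothing requires it. The opening of Section 11 places the interview on the day of, or within a week of, being seen in the ED, which suggests a time after the contact.

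**The case against.** The strongest reply is that staged consent is deliberate. It was developed with people with lived experience, and verbal consent comes first to spare patients at the worst moment. That stands as a reason for staging. It does not explain why Section 9 gives the reverse order, or how the written condition on filming is then met.

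A reader might infer that the ED video cannot be made at all, or that patients would be filmed with no consent. The documents do not support either reading:

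- Section 9's order permits the video.
- In Sections 7 and 8, verbal consent precedes the assessment.
- The Covid-19 paragraph does not place written consent after the assessment, and it accepts audio-recorded verbal consent where written consent is not possible.
- An on-site researcher may take the Step 1 consent in either type of site. That can bring the explanation forward, although Step 1 consent is described as verbal.
- Section 8, item 3, says the information sheets also explain the recordings. Those sheets are not in the text available, so what patients learn before filming cannot be judged.

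Nor would missing video remove all fidelity data. Meeting notes, a contact diary, checklists and audio of follow-up calls are also planned, and WP3 relies on recordings only as far as they can be collected.

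A reader might also infer that a late baseline would understate the treatment effect or give a wrong standard deviation or correlation for the future trial. The protocol specifies no change score, baseline adjustment or such estimate. WP2 (3) aims at acceptability, burden, response rates and feedback, and the only trial sample-size assumption given is a 30% rate of repeat self-harm over 18 months. The first questionnaire set also includes the Helping Alliance Scale and a questionnaire on the ED experience. Both presuppose contact, so part of the timing may be intended, though the protocol does not say so.

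**Conclusion.** The contradiction in consent order and step count is real and lies in the current text. If sites follow Sections 7 and 8 as written, the ED meeting would usually be filmed before the written consent that WP2 Methods require, or the recording would be lost. About 30 recordings are exposed. That number assumes that the Section 7 and 8 order is followed and that written consent is not brought forward. It is wrong as written and should be corrected.

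The baseline point is secondary and conditional. Under the same order, up to 45 intervention-arm patients would complete the first questionnaires after their first intervention contact. It cannot be said that all 60 patients are affected, because Section 9's order would allow earlier completion and control patients receive no enhanced assessment. No power, significance level or efficacy conclusion changes, since this is a feasibility study.

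**What to change.** 1. Rewrite Section 7 (Patients), Section 8 (items 1 and 3) and Section 9 (Consent) to give one order and one number of steps.
2. Make WP2 (4) Methods and the Audio/video recordings paragraph of Section 11 name the same form of consent for recording.
3. Obtain that recording consent before filming starts. It may be written, electronic or audio-recorded. The Covid-19 paragraph already provides for these formats, but it keeps audio-recorded consent for cases where written consent is not possible, so any wider use should be stated. Delete the recording if full consent is later declined.
4. In WP2 (3), log when each first questionnaire is completed relative to the ED assessment, and do not carry those scores into the trial design as pre-intervention values.

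The cost is amendment wording and a short consent form. For patients it is a few minutes at a difficult moment, and possibly some refusals to be filmed. The timing log needs one extra field on the case report form.
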